Title: Effects of Digital Stories Intervention on Psychosocial Well-being for Cancer Patients and Caregivers undergoing Hematopoietic Stem Cell Transplantation (HCT) PI: [name]

ASU: [name], [name], [name]
Mayo: [name]; Consultant: [name]

Award number: R15CA213035 to Arizona State University by National Cancer Institute of the National Institutes of Health

NCT number: NCT03654599

Date: 9/21/2023

Scientific Background

Patients undergoing hematopoietic stem cell transplantation (HCT) are at particular risk for reduced psychosocial well-being. The process is extremely rigorous, requiring relocation to a transplant center, and is associated with multiple acute medical and psychosocial sequelae. HCT patients often report anxiety, depression, and social isolation due to the intense and aggressive transplant experience, such as prolonged recovery and multiple post-HCT complications that result in frequent hospitalizations. Caregivers of HCT recipients also experience high levels of psychosocial distress due to stressors such as caregiving responsibilities and beyond, plus deep concern for their loved ones. Interventions that help cancer patients authentically express and disclose their emotions through supportive open dyadic communication with caregivers have been found to be effective for reducing emotional distress, but time and resources to access professional services are often severely limited. Thus far, however, interventions to alleviate psychosocial distress for both patients and caregivers after HCT have been rare and have yielded inconclusive results.

A narrative-based (storytelling) approach may be an effective intervention tool for HCT patients and caregivers coping with psychosocial distress. Although narratives have been applied and tested to influence health behavior in cancer education and care, there have been only a few rigorous tests of narrative effects for therapeutic purposes, and none of this research has been conducted with HCT patients and caregivers.

Our preliminary data show that stories shared by individuals in which a range of emotional expressions or resolutions are described may have beneficial effects on emotional well-being. In a pilot study with breast cancer patients, participants who viewed digital stories about others coping adaptively with emotions showed reduced emotional distress. In a recent pilot study of a 3-day digital storytelling workshop, we produced a series of digital videos with narratives from a panel of HCT survivors. **We propose to use these digital stories (DS), to be viewed and discussed by HCT patient/caregiver dyads, as a therapeutic intervention and to examine the influences on their psychosocial status.** This low-cost, non-invasive, and easy-to-deliver psychosocial support vehicle has never been formally tested as an intervention for HCT patients or patient-caregiver dyads.

Design and Methods

To build upon our preliminary studies and to pilot test the efficacy of this series of DS, 110 adult patients undergoing HCT at the Mayo Clinic Arizona and their respective adult caregivers (N=220 total participants) were randomized to either (a) an intervention using DS (dyadic exposure to four 5-minute modules) or (b) an information control (IC) video group (dyadic exposure to four videos containing *only information* about post-HCT care) followed by encouragement to discuss as a dyad. Exposure occurred once per week over 4 weeks via a secure web-based data collection platform (REDcap) with a weekly email notification and reminder phone call. Participants completed questionnaires at baseline (T1), after the 4-week intervention (T2), and 3 months (100 days) later (T3). Using our model of ***Narrative Effects on Socio-Emotional Well-Being***, we also examined expected mediating factors to determine how stories may "work" to reduce psychosocial distress by fostering emotional processing, acceptance, vicarious emotional expression and dyadic disclosure of emotions.

Objectives and Aims

Specific Aim 1: To test whether DS are more efficacious for improving psychosocial well-being in patient-caregiver dyads after HCT than an information-only control (IC) condition. Emotional outcomes were measured using the Profile of Mood States (POMS), and social outcomes were measured using the Functional Assessment of Cancer Therapy-General (FACT-G) social well-being scale.

Primary Hypothesis 1: HCT patients and caregivers exposed to DS (intervention arm) will experience less psychosocial distress than those exposed to the information videos (IC arm) at post-intervention (4 weeks, Time 2) and at 3-month post-intervention follow-up (Time 3).

Exploratory Question (EQ) 1: How do DS influence patients and caregivers (differently and/or similarly) in their experience of psychosocial distress, expressed through qualitative in-depth interviews (n=20)?

Specific Aim 2: To examine potential mediators and moderators of the influences of DS on psychosocial well-being in HCT patients and caregivers.

EQ2: What factors (e.g., age, gender, types of other support, treatment) moderate responses to the DS?

EQ3: Do hypothesized mediating variables explain the effects of DS on psychosocial distress, including transportation (i.e., getting carried away by the stories for vicarious emotional expression), emotional processing, identification with DS, and the disclosure of emotions between patients and caregivers?

Specific Aim 3: To employ an existing mentorship program with the Barrett Honors College at Arizona State University that will expose undergraduate nursing students to behavioral and psychosocial oncology research.

IMPACT: We expect DS to be useful to HCT patients and caregivers and to foster improved psychosocial well-being by providing relevant, enriching stories that help the dyads face emotional challenges. Testing the efficacy of narrative-based stories to reduce distress, improve quality of life, and reduce mortality and morbidity rates in HCT patients serves as a critical first step in our larger program of research. If this investigation is successful, we will develop a DS intervention for people with other cancers and in other languages to **reproduce and extend** the study for even broader dissemination of this potentially distress-relieving tool.

Title: Effects of Digital Stories Intervention on Psychosocial Well-being for Cancer Patients and Caregivers undergoing Hematopoietic Stem Cell Transplantation (HCT) PI: [name]
ASU: [name], [name], [name]
Mayo: [name]; Consultant: [name]

Award number: R15CA213035 to Arizona State University by National Cancer Institute of the National Institutes of Health

NCT number: NCT03654599

Date: 9/21/2023

Analysis Plan

Preliminary Analyses. We first used univariate and bivariate statistics to determine the distributional characteristics of our outcome measures, explore patterns of missingness, and identify potentially relevant background confounders and covariates. Where appropriate, we also computed reliability estimates (e.g., Cronbach's α , McDonald's ω_T) for composite measures.

Specific Aim 1: To test whether DS are more efficacious for improving psychosocial well-being in cancer patient-caregiver dyads after HCT than an information-only control (IC) condition.

Aim 1 Analyses. To address hypotheses under **Aim 1**, we used a **scientifically rigorous** dyadic structural equation path model (SEM) approach in which the patient-caregiver dyad is the unit of analysis. We estimated dyad member-specific intervention effects (β_p and β_{cg}) on each outcome simultaneously in a single SEM, by relating arm (DS vs. IC) to each member's T2 (or T3) score on the outcome, adjusting for that member's T1 score on the same outcome measure (Figure 2). Intra-dyad correlation of responses is explicitly accounted for (see curved "paths" in Figure 2). Relevant baseline covariates (e.g., treatment type) identified in preliminary analyses were adjusted for by relating them to T2 outcomes. To explore intervention effects net of potential partner effects (e.g., T1 patient outcome scores predicting change in caregiver scores and vice versa: $\beta_{p,cg}$ and $\beta_{cg,p}$, [see Figure 3]), we extended our dyadic SEMs with an Actor-Partner Interdependence Model (APIM) approach. Partner effects can themselves be of interest, as they may capture potentially important relations underlying dyadic communication and emotional support processes. For outcomes that are unique to one dyad member or the other, a conventional ANCOVA-type approach was taken, where T2 (and T3) outcome scores are regressed on Group, adjusting for T1 scores on the corresponding outcome and relevant background covariates. Under **Aim 1 (EQ1-Qualitative)**, the constructivist approach to grounded theory methodology was employed, guided by EQ1 and a model of narrative effects on socio-emotional well-being. Students under the supervision of [name] transcribed in-depth interview recordings and conduct the analysis using the audio-recordings,

Figure 2

[figure not shown]
[figure not shown]

Figure 3

transcripts, memos, and interview notes. Coding and categorization were undertaken using NVivo, which facilitates the development of a cross-group thematic framework while allowing the continual checking of the contextual validity of individual comments or excerpts of discussion. When categorization is complete, axial coding was performed to elicit overarching themes and promote the exploration of relationships between emergent themes with three experienced researchers until agreement on the assigned codes is reached.

Specific Aim 2: To examine potential mediating and moderating factors proposed in a model to explain the influences of DS on psychosocial well-being in HCT patients and caregivers.

Aim 2 Analyses. To address **EQ2** under **Aim 2**, we extended the models used under Aim 1, by including and testing for the interactions between Group (DS vs. IC) and potential moderators (*age, gender; use of other support services*) to determine if the intervention effects differ across levels of these factors after adjusting for relevant background covariates identified in preliminary analyses. Interaction effects significant at $p < .10$ will be probed so that the form of the interaction (i.e., differences in magnitude and/or sign of the intervention effect across levels of each potential moderator) can be characterized. To address **EQ3** under **Aim 2**, we evaluated indirect effects of the intervention (Group) on outcomes (e.g., emotional and social well-being) through putative mediators (e.g., identification, transportation, and emotional processing and expression), selected based on the proposed Narrative Effects model [see Figure 1] in dyadic SEMs (general form: Group → Mediator [T2] → Outcome [T2 or T3]), adjusting for relevant background covariates identified in preliminary analyses. We used methods and software applications described and developed by Valeri and VanderWeele, which expand on the work of Preacher and Hayes. From these analyses we obtained estimates and tests (based on bootstrap standard errors) of the indirect effects of the intervention on primary and secondary outcomes via hypothesized mediators (e.g., identification, engagement, emotional support). We also used methods and tools described and developed by Preacher and Kelley⁸² to characterize the magnitudes of the indirect effects examined.

Missing Data and Non-compliance. We employed an ITT analysis strategy and mitigate potential effects of attrition on estimates of treatment effects and statistical power by using full information maximum likelihood estimation and/or multiply imputed datasets, depending on patterns of missingness observed and the analytic model used. To explore potential impacts of intervention non-compliance (e.g., not viewing all DS) on estimates of intervention effects, we used complier-average causal effect (CACE) and propensity score (PS) methods, which model and adjust for non-compliance, and then compare ITT, CACE, and PS-based estimates.

Data Management. All data forms were designed using uniform principles that have been employed in many of our studies and that are intended to minimize coding. We performed 100% visual comparison of primary outcome items from the database against the paper forms. After data entry, operational reports were generated that (1) document the completeness with which forms are being collected and (2) for every item on every form, report the number and percentage of missing values.

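### EQ3 tests indirect effects from bootstrap standard errors and names no asymmetric interval; adding a percentile interval is a cheap improvement that recovers power at many small-to-medium paths

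*SAP*

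**What the plan says.** The protocol's Objectives and Aims section poses EQ3 as an exploratory question: "Do hypothesized mediating variables explain the effects of DS on psychosocial distress". Under Aim 2 Analyses, the SAP answers it in dyadic structural equation models with a chain from Group to a T2 mediator to a T2 or T3 outcome. On inference it says that the analyses gave "estimates and tests (based on bootstrap standard errors) of the indirect effects of the intervention on primary and secondary outcomes via hypothesized mediators". It refers to published mediation methods and software, and to separate tools for the size of the indirect effects.

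Neither document names a percentile, bias-corrected or other asymmetric interval. Neither gives a test formula or a significance level for EQ3. The only threshold printed is for the EQ2 moderators: "Interaction effects significant at $p < .10$ will be probed".

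The protocol's Design and Methods section gives the size as "110 adult patients undergoing HCT at the Mayo Clinic Arizona and their respective adult caregivers (N=220 total participants". Under the SAP's Aim 1 Analyses "the patient-caregiver dyad is the unit of analysis", so each member-specific path rests on at most 110 observations. Missing data are handled by full information maximum likelihood (FIML), multiple imputation, or both.

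**The concern.** The indirect effect is the product a × b, where a is the Group-to-mediator path and b the mediator-to-outcome slope. Unless at least one path is large relative to its standard error, the estimate of that product is skewed. A test that divides it by a standard error and uses normal critical values ignores the skew and rejects too rarely. The resamples that supply the bootstrap SE also supply the quantiles for an interval that follows the skew, so the better method costs almost nothing.

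EQ3 is the trial's quantitative test of its narrative-effects model. At stake is a real mediator that fails to reach significance and is then set aside before the larger programme of research that the protocol describes.

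**Working it through.** **Inputs.** From the documents: 110 dyads, the dyad as unit, the product form of the indirect effect, and tests based on bootstrap SEs. The plan has no power figure for EQ3 to reproduce. Assumed: 1:1 allocation, residual SD 1, two-sided 5%, and the path sizes (a in residual-SD units, b per unit of mediator).

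**Why the SE test falls short: one worked pair.** At (a,b) = (.4,.3) and n = 110:
- SE(a) ≈ 2/√110 = 0.191, so a/SE(a) = 2.10.
- SE(b) ≈ 1/√110 = 0.095, so b/SE(b) = 3.15.
- Var(ab) ≈ a²·SE(b)² + b²·SE(a)² + SE(a)²·SE(b)² = 0.00145 + 0.00327 + 0.00033 = 0.00506, so SE(ab) = 0.071.
- ab/SE(ab) = 0.12/0.071 = 1.69.

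Each path alone lies beyond 1.96 at its expected value, but the ratio for the product does not.

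**Simulation.** M = a·G + e and Y = b·M + 0.5·Y(T1) + e, fitted by least squares with G and Y(T1) as covariates; 10,000 trials × 1,000 resamples (Monte Carlo SE at most 0.5 points for power). Rule 1: |ab/SE_boot| > 1.96. Rule 2: the 95% percentile interval excludes 0. Losses are differences of the printed figures.

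| (a,b) | SE test | Percentile | Loss, points |
|---|---|---|---|
| (.3,.2) | 6% | 16% | 10 |
| (.3,.3) | 14% | 29% | 15 |
| (.4,.3) | 25% | 46% | 21 |
| (.5,.2) | 18% | 38% | 20 |
| (.5,.3) | 40% | 63% | 23 |
| (.6,.4) | 74% | 86% | 12 |
| (.2,.2) | 2% | 8% | 6 |
| (.5,.1)* | 3.3% | 10.8% | 7.5 |
| (.3,.1)* | 2.1% | 5.8% | 3.7 |
| (.5,.5) | 66% | 75% | 9 |
| (.3,.6) | 30% | 35% | 5 |
| (.8,.4) | 92% | 97% | 5 |
| (.8,.5) | 96.8% | 98.5% | 1.7 |
| (.8,.6) | 98.0% | 98.7% | 0.7 |
| (1.0,.6) | 99.8% | 99.9% | 0.1 |

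*Smaller run, 1,500 trials × 600 resamples; Monte Carlo SE at most √(0.108 × 0.892/1,500) = 0.8 points.

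A separately built simulation without the baseline score gave 40.3% against 62.5% at (.5,.3) and 14.2% against 29.8% at (.3,.3).

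**Type I error at nominal 5%.**

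| Null (a,b) | SE test | 95% percentile | 96% percentile |
|---|---|---|---|
| (0,.3) | 1.1% | 4.0% | 3.1% |
| (.5,0) | 0.8% | 3.6% | 2.8% |
| (.8,0) | 2.9% | 5.8% | 4.6% |
| (1.0,0) | 3.8% | 6.0% | 4.8% |
| (0,1.0) | 4.6% | 5.3% | 4.2% |

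One smaller run put the 95% percentile interval at 6.8% with a strong Group-mediator path, so allow for 6-7%.

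**Matched on error.** Across the single-member and dyadic runs, the 96% interval has a highest null error of 4.7-4.8%, against 4.6-4.9% for the SE test. The loss at the small-to-medium pairs is then 8-18 points: (.5,.3) 40% against 58%; (.4,.3) 25% against 41%; (.3,.3) 14% against 25%. At (.3,.6) it is 2.5 points and at (.8,.6) 0.3.

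**Sensitivity at the small-to-medium pairs.**
- Dyadic model (assumed within-dyad correlation .4, whole dyads resampled): loss 10-22 points, for example (.4,.3) 29% against 48%.
- Two-sided 10%: loss 4-19 points, for example (.4,.3) 44% against 60%.
- Assumed 88 dyads (20% loss), 5%: loss 8-23 points, for example (.4,.3) 16% against 34%; at (.8,.6) the loss is 2.8.

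**Expected false positives.** Assume 3 mediators × 2 outcomes × 2 time points × 2 members = 24 indirect effects, each with one zero path. SE test: 24 × 0.8% to 24 × 4.9% = 0.2 to 1.2. 95% percentile: 24 × 3.6% to 24 × 6.0% = 0.9 to 1.4.

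**The case against.** The test formula is inferred. The SAP is a short summary that points to outside tools ("We used methods and software applications described and developed by"), and those may already print an asymmetric interval. EQ3 is exploratory, the SE test errs toward fewer claims of mediation, and the plan also reports estimates and magnitudes. The SAP is written largely in the past tense ("From these analyses we obtained estimates and tests"), so a percentile interval would probably be a more liberal rule added after results exist. All of this stands, and it limits the point to a modest one. It does not remove it: no asymmetric interval is named, and the gain persists when null error is matched.

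Three stronger readings are tempting.
- **A general loss of 10-23 points.** The documents give no path sizes, and several plausible pairs lose only 3-9 points. Nor is the loss negligible for every strong pair: (.8,.4) still loses about 5.
- **Damage to the trial's main conclusion.** Primary Hypothesis 1 is tested by the Aim 1 models, which do not use this test.
- **Non-significance will be read as no mediation.** Nothing in the SAP says so. The sentence proposed below is a safeguard, not a correction of a stated rule.

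**Conclusion.** The point holds as a cheap improvement to an exploratory analysis. If the EQ3 test is estimate over bootstrap SE against a normal reference, then at 110 dyads and two-sided 5% it gives up about 10-23 points of power to a 95% percentile interval at many small-to-medium pairs. It gives up about 3-9 points when one path is very small or when b is large with moderate a. The loss is about 5 points at (.8,.4), 1-2 at (.8,.5), and under 1 only at about (.8,.6) and above. When one path is zero and the other moderate, it runs near 1% error instead of 5%, so its non-significance alone says little about absence of mediation.

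These figures rest on assumed paths, allocation and alpha, on complete data, and on models without extra covariates or partner effects. The direction held in every setting run; the size depends on paths that the documents do not give.

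**What to change.** Add to the SAP's Aim 2 Analyses, under EQ3:

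> For every indirect effect tested we report the estimate, the bootstrap SE with its test, and the percentile bootstrap interval from the same whole-dyad resamples. All indirect effects tested are listed. A non-significant SE-based test alone is not read as absence of mediation.

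- **If the analysis is not yet run:** base inference on the percentile interval. A 96% interval kept null error under 5% in the settings run and retained most of the gain.
- **If it is already run:** label the interval as an added exploratory analysis, keep the SE test as the planned result, and report any effect on which the two disagree as inconclusive. That rule stops the added interval from displacing the planned result.
- **If the software already output such an interval:** name it and report it.

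**Cost.** Under FIML, two or three sentences and extra output from existing resamples, or one re-run if the resamples were not kept or did not hold dyads together. Under multiple imputation, more computing. The 95% interval also brings the slightly higher exploratory false-positive count and the null error of up to about 6-7% noted in the working.

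### If only dyads who viewed all four stories count as compliers, does the exploratory CACE need an any-viewing CACE beside it?

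*SAP*

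**What the plan says.** The SAP section Missing Data and Non-compliance sets the main strategy: "We employed an ITT analysis strategy". It then adds an exploratory step: "To explore potential impacts of intervention non-compliance (e.g., not viewing all DS) on estimates of intervention effects, we used complier-average causal effect (CACE", paired with "propensity score (PS) methods, which model and adjust for non-compliance, and then compare ITT, CACE, and PS-based estimates". Incomplete viewing of the stories appears only as a bracketed illustration of non-compliance. The section gives no number of modules that makes a complier, no CACE estimator and no exclusion restriction. It also does not say whether compliance is judged per member or per dyad.

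The Protocol, Design and Methods, describes the intervention as "dyadic exposure to four 5-minute modules" and its timing as "Exposure occurred once per week over 4 weeks via a secure web-based data collection platform (REDcap". A dyad could therefore view one, two or three modules. The control arm is active: "dyadic exposure to four videos containing *only information* about post-HCT care". The SAP's Aim 1 Analyses use a path model "in which the patient-caregiver dyad is the unit of analysis", with a separate intervention effect for each member.

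**The concern.** A four-part intervention produces partial exposure. A CACE with a yes/no complier definition has to put partial viewers on one side of the line. If the line is all four modules and non-compliers are assumed to have no effect, the whole ITT effect is attributed to the full viewers, including whatever partial viewers gained. The CACE then overstates the benefit of full viewing whenever partial viewing helps. A reader could take the gap between ITT and CACE as the cost of non-compliance when part of it comes from where the line was drawn. A second CACE, counting any dyad that viewed at least one module as a complier, looks like a cheap way to show the range.

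What is at stake is the reading of one exploratory comparison.

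**Working it through.** **Inputs from the documents.** 110 dyads and four weekly modules (Protocol, Design and Methods); ITT, CACE and PS-based estimates to be compared (SAP, Missing Data and Non-compliance). The documents give no viewing rate, effect size or CACE figure, so there is no planned figure to reproduce.

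**Assumptions.** Let p_all and p_part be the shares of DS dyads viewing all four and one to three modules. Let E be the full viewers' effect, set at -0.50 SD, and f the partial viewers' effect as a share of E. Dyads that would view nothing are taken to have no effect.

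**Formulas.**
- ITT = E × (p_all + f × p_part)
- All-four CACE = ITT / p_all = E × (1 + f × p_part / p_all)
- Any-viewing CACE = ITT / (p_all + p_part)

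**Results at f = 0.5.**

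| p_all / p_part | ITT | Any-viewing | True E | All-four | All-four ÷ E |
|---|---|---|---|---|---|
| 80 / 15 | -0.50 × 0.875 = -0.438 | -0.438 / 0.95 = -0.461 | -0.50 | -0.438 / 0.80 = -0.547 | 1.09 |
| 60 / 30 | -0.50 × 0.75 = -0.375 | -0.375 / 0.90 = -0.417 | -0.50 | -0.375 / 0.60 = -0.625 | 1.25 |
| 50 / 40 | -0.50 × 0.70 = -0.350 | -0.350 / 0.90 = -0.389 | -0.50 | -0.350 / 0.50 = -0.700 | 1.40 |

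The over-credit is therefore real under these conditions. If f = 0 the all-four CACE equals E at any viewing rates.

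**What the plan already shows.** When f lies between 0 and 1 and zero-viewers have no effect, the magnitudes are ordered ITT ≤ any-viewing CACE ≤ E ≤ all-four CACE. The ITT and the all-four CACE, both already planned, enclose E in expectation in every row.

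**What the extra CACE adds.** It moves the lower limit by 0.461 - 0.438 = 0.023, 0.417 - 0.375 = 0.042 and 0.389 - 0.350 = 0.039 SD. With 110 dyads, assumed 1:1 allocation and a baseline correlation of 0.6, the standard error of the ITT estimate is about √(1 - 0.36) × √(4/110) = 0.8 × 0.191 = 0.15; simulation under the same set-up gave 0.16. The gain is at most about a quarter of a standard error.

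The ratio of the two CACEs is (p_all + p_part) / p_all, that is 1.19, 1.50 and 1.80 in the three rows, whatever f is. Given the viewing rates, either CACE can be computed from the other, so the second holds no further outcome information.

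**How often the point estimates straddle E.** In simulations of 20,000 trials at half benefit, the planned pair (ITT and all-four CACE) did so in 25%, 48% and 58% of trials for the three rows. The pair of two CACEs did so in 19%, 37% and about 48%. The proposed pair is narrower and contains the truth less often.

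**Where the bracket fails.**
- *Partial viewers gain more than full viewers.* At 60/30, with a benefit of 0.40 in full viewers and 0.60 in partial viewers, ITT is 0.42, any-viewing 0.467 and all-four 0.70, all above 0.40.
- *Partial viewing harms.* With -0.20 in partial viewers, the three are 0.18, 0.20 and 0.30, all below 0.40.
- *Zero-viewers have an effect.* The control is active, so dyads who would view no stories might still watch the information videos. At 60/30/10 with f = 0, E = -0.50 and an assumed zero-viewer contrast of +0.10, ITT = -0.30 + 0.01 = -0.29, any-viewing = -0.322 and all-four = -0.483. All fall short of -0.50.

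In each of these cases adding the any-viewing CACE does not repair the bracket.

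**The case for a change.** The strongest case for a change is that the SAP leaves open what is needed to interpret any CACE: who is a complier, which estimator is used and what is assumed about non-compliers. Incomplete viewing is its only example, so an all-four cut-off is a natural reading. The over-credit then follows by algebra and could reach 40% at 50/40 viewing. The ITT is a looser lower bound than the any-viewing CACE. The PS comparison is a weak guide: at 60/30 with half benefit, the expected gap between the CACE and a PS-type estimate is -0.13 with a standard deviation of 0.15, and it is informative only if viewing is unconfounded. A recode and a rerun cost little.

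The silence on definitions stands, and so does the algebra. The rest carries less weight. An illustration is not a cut-off, and a CACE model that relaxes the exclusion restriction would not follow the formula. The over-credit is about a quarter of the CACE's own standard error at 80/15 (0.047 / 0.19), half at 60/30 (0.125 / 0.26) and 0.6 at 50/40 (0.20 / 0.32). The low cost also assumes that viewing was logged per module, which the documents do not confirm. A dyad-level rule would still have to say whether both members or either must have viewed.

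**Conclusion.** No change to the plan. The gap is missing detail in an exploratory analysis. Analysts cannot run a CACE without choosing a compliance rule and an assumption about non-compliers, and a report of the result would ordinarily state both together with the number of modules viewed. With those viewing rates and the planned ITT-to-CACE comparison, a reader can already see how far the full-viewer effect depends on what partial viewing does.

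The any-viewing CACE would tighten the lower limit by 0.02 to 0.04 SD in the scenarios examined, against a standard error of about 0.16, and would add no outcome information. These sizes rest on assumed viewing rates, half benefit in partial viewers, a true effect of -0.50 SD, 1:1 allocation and a baseline correlation of 0.6. Bracketing, with either pair, also requires that partial viewers gain between nothing and the full effect, and that assignment makes no difference to dyads who would view no stories. The ITT test of Primary Hypothesis 1 does not depend on any of this.
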